#### 6.2 Dosage and Administration

Subjects in the first dose-level cohort will be assigned to receive M3541 at a starting dose of 50 mg orally once per FD, which will be given 1 hour and 45 minutes ( $\pm$  60 minutes) before RT fraction. The dose of M3541 can be changed from 1 cohort to another according to the dose-escalation rules described in Section 5.1 for the different dose levels and dosing regimens. No intrasubject dose escalation / de-escalation is permitted.

Subjects will be asked to arrive at the clinic  $\geq 2$  hours prior to scheduled RT on M3541 treatment days, having had a light breakfast, and will be administered M3541 at the clinic 1 hour and 45 minutes ( $\pm$  60 minutes) before RT is started. Subjects will take their assigned dose of M3541 with a full glass of water (approximately 240 mL or 8 fluid ounces).

The subsequent doses should not be taken until the predose PK and pharmacodynamic (as appropriate) blood collection has been completed.

If a subject vomits after taking their dose of M3541, they should be given an antiemetic but no further dose will be given that day. Prophylactic antiemetics should then be given before subsequent doses of M3541. Any change from the dosing schedule, ie, dose interruptions, should be recorded in the eCRF.

# 6.2.1 General Dose Modification and Discontinuation Guidelines

There is no intrasubject dose reduction or escalation planned for M3541. In general, each subject will stay on M3541 at the dose level and schedule assigned at study entry unless treatment needs

Document No. CC

Object No. CC

to be interrupted or stopped. If the Investigator believes that a TEAE is due to RT, M3541 will also be stopped.

Maximum delays or M3541 administrations missed within the complete 10-FD treatment period are:

- For the once per FD schedule:
  - If RT and M3541 treatment must be interrupted for ≥ 4 FDs, subjects must be discontinued from M3541
- For the thrice weekly schedule:
  - If M3541 cannot be administered on the scheduled day / time, the M3541 dose will be skipped
  - If RT and M3541 treatment must be interrupted for ≥ 2 FDs, subjects must be discontinued from M3541
- For the twice weekly schedule:
  - If M3541 cannot be administered on the scheduled day / time, then M3541 administration should until 24 hours later, and if not possible, the dose will be skipped
  - If RT and M3541 treatment must be interrupted for ≥ 1 FDs, subjects must be discontinued from M3541

M3541 should not be administered if no radiotherapy is scheduled for that day. If the subject must be discontinued from M3541; RT can be resumed at the discretion of the Investigator.

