# 5.1.1 Dose-limiting Toxicity

For this study, a DLT is defined as any of the following AEs that occur during the DLT evaluation period (except those that are clearly and incontrovertibly due to disease progression or extraneous causes), with severity graded according to the National Cancer Institute (NCI) Common Terminology Criteria for Adverse Events, Version 4.03 (CTCAE V4.03):

- Grade  $\geq$  3 non-hematologic toxicity, except:
  - $\circ$  Nausea, vomiting and / or diarrhea lasting  $\leq$  3 days in the once per FD and twice weekly schedules or 2 days in the thrice weekly schedule that can be medically managed
  - Worsening of pre-existing tumor pain associated with tumor lesions for which the subject is irradiated in the context of this study
- Evidence of treatment-related hepatocellular injury for > 3 days in the once per FD and twice weekly schedules and 2 days in the thrice weekly schedule, such as ≥ 5 × the upper limit of normal (ULN) of alanine aminotransferase (ALT) or aspartate aminotransferase (AST) and without any other apparent clinical causality
- Any occurrence of Hy's law (defined as aminotransferases > 3 × ULN, alkaline phosphatase < 2 × ULN, total bilirubin ≥ 2 × ULN, with no other reason to account for these abnormalities)
- Febrile neutropenia or Grade 4 neutropenia lasting for > 5 days, Grade 4 thrombocytopenia or any requirement for platelet transfusion (as defined by Grade 4 thrombocytopenia lasting for > 5 days or Grade ≥ 3 thrombocytopenia with bleeding), Grade 4 anemia that is unexplained by the underlying disease
- Any toxicity related to study treatment that causes the subject to interrupt treatment (defined as having to delay the next scheduled M3541 administration) for:
  - $\circ \geq 4$  FDs in the once per FD dosing schedule.
  - $\circ$  > 1 FD in the thrice weekly schedule
  - not to be able to be treated within 24 hours of the scheduled treatment time in the twice weekly schedule
- A related treatment-emergent adverse event (TEAE) that in the opinion of the SMC is of potential clinical significance such that further dose escalation would expose subjects to unacceptable risk.

Information on DLTs will be sent by the Sponsor or delegate to the SMC core members within 1 working day of the receipt of documented information.

Document No. CC Object No. CC

Dose escalation of M3541 will start from 50 mg orally once per FD until 1 of the following stopping rules apply:

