# 5.5 Criteria for Subject Withdrawal

#### 5.5.1 Withdrawal from Study Therapy

The subject must be withdrawn from M3541 in the event of any of the following:

- Withdrawal of consent
- Development of unacceptable toxicity
- Occurrence of progressive disease (PD) according to Response Evaluation Criteria in Solid Tumors version 1 (RECIST 1.1) or initiation of any other anticancer therapy
- Occurrence of any condition that is clinically relevant and affects the subject's safety, if discontinuation is considered necessary by the Investigator and / or Sponsor prior to treatment completion
- TEAEs that cause a treatment delay of > 3 FDs of radiotherapy.
- Occurrence of RT-related Grade ≥ 3 AEs, or any AE if discontinuation of IMP is desired or considered necessary by the Investigator and /or the subject (if applicable)
- Occurrence of pregnancy
- Use of a non-permitted concomitant drug (including any other drug with known anticancer activity unless specified otherwise in Section 6.5.2)
- Noncompliance that is deemed by the Investigator or the Sponsor to compromise subject safety or study integrity.

Planned tumor assessments will continue as scheduled if a subject does not complete the protocol defined study therapy (unless subject withdraws consent).

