#### 6.4 Noninvestigational Medicinal Products to be Used

#### 6.4.1 Radiotherapy

Radiotherapy will follow institutional guidelines with the first day of RT treatment on a Monday (FD 1). The total dose of RT is 30 Gy given in 10 daily fractions (ie, 3 Gy/FD, 5 FDs per calendar week, FD 1 to FD 10 over a 2-calendar week period). An interruption in the administration of RT will result in an interruption of M3541 for as long as the RT is interrupted (see Section 6.2.1).

All effort should be made to complete 10 FDs if possible. The formal criteria for dose modification in the study are included in Table 7. The study site will provide the Sponsor with irradiation simulation details when required.

Document No. CC Object No. CC

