#### Table 7 Dose Interruption for M3541 and Radiotherapy

	Dose Modifica	ations		
Toxicity	M3541ª	Radiotherapy b		

 
Toxicities in Radiation Field
 
Observations occurring in field of irradiation (which can't be explained by the disease or any other extraneous cause) such as mucositis, radiation dermatitis, cystitis, proctitis, nausea, vomiting, etc
 
	Grade 3 Permanently discontinue M3541. In case of liver-related transaminase increases, treatment should be permanently discontinued unless the transaminase rise is undeniably due to major tumor response. Grade 4 Permanently discontinue M3541	Temporarily interrupt RT during M3541 interruption. If interruption is longer than allowed in Section 6.2.1, RT without M3541 can be resumed at the discretion of the Investigator.		
Systemic Toxicities Considered to be Unrelated to RT, Hematologic				

 
Hematologic Toxicities: Any Grade ≥ 3 toxicity, excluding:
 
	Temporarily interrupt treatment. Resume treatment (at the same	Temporarily interrupt RT during M3541 interruption. If		

 
Neutropenia lasting for ≤ 5 days and not associated with fever
 
	dose) once severity resolves to Grade $\leq$ 1 or baseline. See	interruption is longer		

 
Isolated Grade 4 lymphocytopenia without clinical correlate
 
	Section 6.2.1 for dose delay allowances.	than allowed in Section 6.2.1, RT without M3541 can be		
Grade 3 thrombocytopenia without bleeding		resumed at the		
Any grade of anemia		discretion of the Investigator.		
Systemic Toxicities Considered to be Unrelated to RT, Hepatocellular				

 
Treatment-related hepatocellular injury for more than 3 days, such as Grade ≥ 3 ALT or AST (≥ 5 × ULN) with or without elevation of serum total bilirubin to > 2 × ULN, without initial findings of cholestasis (elevated serum alkaline phosphatase) or other apparent clinical causality.
 
	Temporarily interrupt treatment. Resume treatment (at the same dose) once severity resolves to Grade ≤ 1 or baseline. See Section 6.2.1 for dose delay allowances.	Temporarily interrupt RT during M3541 interruption. If interruption is longer than allowed in Section 6.2.1, RT without M3541 can be resumed at the discretion of the Investigator.		

CCI

	Dose Modific	ations
Toxicity	M3541ª	Radiotherapy b

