#### 8.4 Analysis Sets

For purposes of analysis, the following populations are defined:

- Screened Analysis Set: All subjects who signed an ICF
- **DLT Analysis Set**: All subjects who received at least 1 dose of M3541 and meet at least 1 of the following criteria:
  - Experienced at least 1 DLT during the DLT evaluation period, regardless of the number of doses of M3541 administered
  - For the M3541 once per FD:
    - Received at least 80% of planned dose of each treatment, ie, 8 fractions of RT and 8 of 10 M3541 administrations during the treatment period
  - For the M3541 thrice weekly schedule:
    - Received at least 80% of planned dose of each treatment, ie, 8 fractions of RT and 5 of 6 M3541 administrations during the treatment period
  - For the M3541 twice weekly schedule:
    - Received at least 80% of planned dose of RT and all 4 M3541 administrations during the treatment period

In addition, subjects without DLT must have completed the DLT follow-up period, ie, having a safety assessment on PTD 15 (allowing for a window of + 2 days).

- Safety Analysis Set: All subjects who receive at least 1 dose of study treatment (M3541). Subjects will be analyzed according to the actual treatment (ie, dose) they receive
- **PK Analysis Set:** All subjects who receive at least 1 dose of M3541 and have at least 1 measurable plasma concentration at a scheduled PK time point post dose. Data from subjects with a vomiting episode within 2 times of tmax for M3541 (about 4 hours postdose in total) may be excluded from the PK analysis set on the case-by-case basis
- **Biomarker Analysis Set:** All subjects who received at least 1 dose of study treatment and have provided at least a blood and / or tumor sample prior to any M3541 treatment, or at least 1 post-treatment blood sample.

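### Three protocol passages give different M3541 stopping rules for a mild reaction attributed to RT, and the rule a site follows can decide whether the subject counts for the DLT analysis

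*Protocol*

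**What the plan says.** Protocol Section 6.2.1: "If the Investigator believes that a TEAE is due to RT, M3541 will also be stopped". No grade and no discretion are stated.

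Protocol Section 5.5.1 lists among the events that require withdrawal from M3541: "Occurrence of RT-related Grade ≥ 3 AEs, or any AE if discontinuation of IMP is desired or considered necessary by the Investigator" (or the subject, where applicable). Withdrawal is thus mandatory from Grade 3 and discretionary for any other AE.

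Protocol Table 7, in-field row: "Grade 3 Permanently discontinue M3541", and the same action at Grade 4. No M3541 action is listed for Grade 1 or 2. Section 6.4.1 gives the table its standing: "The formal criteria for dose modification in the study are included in Table 7".

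Two further rules turn lost doses into endpoint status. Section 5.1.1 counts as a DLT: "Any toxicity related to study treatment that causes the subject to interrupt treatment (defined as having to delay the next scheduled M3541 administration) for" at least 4 FDs on the once per FD schedule, with no grade limit. Section 8.4 requires a subject without a DLT to have received "8 fractions of RT and 8 of 10 M3541 administrations during the treatment period". SAP Section 8.2 repeats the 8 of 10 rule, and Protocol Section 5.5.2 replaces subjects who fall outside the DLT Analysis Set.

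**The concern.** Table 7 gives mucositis, radiation dermatitis, nausea and vomiting as its in-field examples. Section 7.4 and the schedule footnotes ask for worsening in an irradiated area to be reported as a TEAE with its grade and its relation to RT or M3541. A low-grade event attributed to RT is therefore an ordinary occurrence in this trial, and it is the event that Section 6.2.1 acts on.

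Two sites can treat the same Grade 1 reaction differently and both be following the protocol. One subject loses the rest of the assigned M3541, while the other may complete it. The primary endpoint is read in cohorts of 3, so one subject made non-evaluable, or counted as a DLT, matters. If in-field reactions become more frequent with dose, as the mechanism in Section 3.1.3 makes plausible, the affected subjects would not be a random subset. The documents do not quantify that.

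**Working it through.** **Step 1: the passages side by side for one event, a Grade 1 or 2 in-field reaction attributed to RT.**

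- Section 6.2.1, read literally: M3541 stops.
- Section 5.5.1: M3541 stops if the Investigator or subject wants it or thinks it necessary.
- Table 7: no M3541 action listed.

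**Step 2: the plan's own threshold.** Section 8.4 asks for at least 80% of planned dose: 0.8 × 10 = 8 administrations. The stated 8 of 10 is reproduced. Only the once per FD schedule is worked here, because SAP Section 7 says the intermittent schedules were never explored.

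**Step 3: stop after k doses.** Assume the stop is permanent. Doses missed = 10 − k. Evaluable without a DLT if k ≥ 8. The length in the interruption criterion is reached if 10 − k ≥ 4, that is k ≤ 6.

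| Doses given (k) | Doses missed | Stop not counted as an interruption DLT | Stop counted as an interruption DLT |
|---|---|---|---|
| 1 to 6 | 9 to 4 | Not evaluable, replaced | DLT |
| 7 | 3 | Not evaluable, replaced | Not evaluable, replaced |
| 8 to 9 | 2 to 1 | Evaluable, no DLT | Evaluable, no DLT |
| 10 (no stop) | 0 | Evaluable, no DLT | Evaluable, no DLT |

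Seven of the nine mid-course stopping points (k = 1 to 7) change the subject's status compared with a full course.

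**Step 4: what the DLT column needs.**

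- A permanent stop must count as an interruption. Section 5.1.1 defines interruption as a delay of the next scheduled administration. Sections 6.2.1 and Table 7 use separate words for interrupting and for stopping or discontinuing.
- Study treatment in Section 5.1.1 must include RT. The causality paragraph of Section 7.4.1.1 includes radiation therapy. The Safety Analysis Set in Section 8.4 uses the term for M3541 alone.
- The Investigator or the SMC must flag the event as a DLT (SAP Section 15.1.1), and the SMC decides how relevant it is for the next dose (Protocol Synopsis, Methodology).

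If either of the first two conditions fails, the subject stopped at k = 1 to 7 is non-evaluable and replaced.

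**Step 5: illustration of what one extra DLT does.** The data are assumed: 0/3 at 50 mg, 0/4 at 100 mg, then 0/3 or 1/3 at 200 mg. The model and priors are those of Section 8.1. The reference dose d_ref is not in the documents, so it is varied. Prob(DLT rate > 35%) at 200 mg, to be compared with the 25% limit:

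| d_ref (mg) | 0/3 at 200 mg | 1/3 at 200 mg |
|---|---|---|
| 50 | 0.07 | 0.23 |
| 100 | 0.09 | 0.32 |
| 200 | 0.08 | 0.26 |
| 300 | 0.01 | 0.08 |
| 500 | 0.004 | 0.04 |
| 800 | 0.002 | 0.03 |

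The limit is crossed at d_ref 100 and 200 mg and not at the other values tried. The table shows the leverage of any single extra DLT in a cohort of 3. It does not show that the sentence in Section 6.2.1 produces one.

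**The case against.** The strongest defence is that the sentence in Section 6.2.1 was never meant as an any-grade rule. It follows a statement that treatment continues unless it must be interrupted or stopped, and the word also may mean that M3541 stops when RT is stopped for the event. The section is headed as general guidance, while Table 7 is called the formal criteria, so a careful site would follow the table. This reading is possible, but the sentence does not say it. Section 6.4.1 and footnote a of Table 7 already cover M3541 during an RT interruption, so the sentence is not needed for that purpose.

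Secondly, Section 5.5.1 already allows a stop at any grade, so some loss of doses after mild reactions would remain whatever Section 6.2.1 said. That stands. It limits how much of the problem can be laid on Section 6.2.1, and it means Section 5.5.1 cannot be described as stopping M3541 only from Grade 3.

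Thirdly, Table 7 is silent on Grades 1 and 2, so a full 10 doses is possible under it but not prescribed. That also stands.

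Finally, the SMC sees all AEs, judges the relevance of DLTs and is not bound by the model, so a Grade 1 event counted through the interruption criterion would be visible to it. This protects the escalation decision in part. It does not restore doses already withheld or return a non-evaluable subject to the DLT Analysis Set.

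**Conclusion.** The inconsistency is in the text and needs no assumption: for a mild RT-attributed event the three passages give a mandatory stop, a discretionary stop and no listed action.

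The firm consequence is for evaluability. Given a permanent stop after 1 to 7 of 10 doses, the subject falls below 8 of 10 and is replaced, unless a DLT is counted. This does not depend on how interruption or study treatment is read.

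A reader might infer that a Grade 1 reaction becomes a DLT whenever it costs 4 or more FDs of M3541. The documents do not support that as a general statement. It holds only for stops after 1 to 6 doses, only if a permanent stop is an interruption and study treatment includes RT, and only with an Investigator or SMC flag. A reader might also infer that the recommended dose is biased. The documents give neither the frequency of such stops nor d_ref, so no size can be put on that.

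**What to change.** Reconcile Section 6.2.1, Section 5.5.1 and the in-field row of Table 7 so that a single rule governs TEAEs attributed to RT, stated the same way in all three. Which rule applies is for the sponsor to decide, and this review takes no position on it. If the sentence in Section 6.2.1 is meant to apply only when RT itself is stopped, it should say so.

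In Section 5.1.1, state whether a stop of M3541 mandated by that rule counts toward the criterion of at least 4 FDs, and whether study treatment there includes RT.

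The cost is protocol wording in these sections and a letter to sites. No visits, assessments or subjects are added.

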#### 6.3 Assignment to Treatment Cohorts

The Investigator or delegate will assign a unique subject identifier number to eligible subjects in chronological order at the time of informed consent signature. Subject identifiers will be comprised of digits representing the study number, the site number, and the subject number, which is allocated sequentially. Subject enrollment will be managed manually.

#### 6.4 Noninvestigational Medicinal Products to be Used

#### 6.4.1 Radiotherapy

Radiotherapy will follow institutional guidelines with the first day of RT treatment on a Monday (FD 1). The total dose of RT is 30 Gy given in 10 daily fractions (ie, 3 Gy/FD, 5 FDs per calendar week, FD 1 to FD 10 over a 2-calendar week period). An interruption in the administration of RT will result in an interruption of M3541 for as long as the RT is interrupted (see Section 6.2.1).

All effort should be made to complete 10 FDs if possible. The formal criteria for dose modification in the study are included in Table 7. The study site will provide the Sponsor with irradiation simulation details when required.

Document No. CC Object No. CC

#### Table 7 Dose Interruption for M3541 and Radiotherapy

	Dose Modifica	ations		
Toxicity	M3541ª	Radiotherapy b		

 
Toxicities in Radiation Field
 
Observations occurring in field of irradiation (which can't be explained by the disease or any other extraneous cause) such as mucositis, radiation dermatitis, cystitis, proctitis, nausea, vomiting, etc
 
	Grade 3 Permanently discontinue M3541. In case of liver-related transaminase increases, treatment should be permanently discontinued unless the transaminase rise is undeniably due to major tumor response. Grade 4 Permanently discontinue M3541	Temporarily interrupt RT during M3541 interruption. If interruption is longer than allowed in Section 6.2.1, RT without M3541 can be resumed at the discretion of the Investigator.		
Systemic Toxicities Considered to be Unrelated to RT, Hematologic				

 
Hematologic Toxicities: Any Grade ≥ 3 toxicity, excluding:
 
	Temporarily interrupt treatment. Resume treatment (at the same	Temporarily interrupt RT during M3541 interruption. If		

 
Neutropenia lasting for ≤ 5 days and not associated with fever
 
	dose) once severity resolves to Grade $\leq$ 1 or baseline. See	interruption is longer		

 
Isolated Grade 4 lymphocytopenia without clinical correlate
 
	Section 6.2.1 for dose delay allowances.	than allowed in Section 6.2.1, RT without M3541 can be		
Grade 3 thrombocytopenia without bleeding		resumed at the		
Any grade of anemia		discretion of the Investigator.		
Systemic Toxicities Considered to be Unrelated to RT, Hepatocellular				

 
Treatment-related hepatocellular injury for more than 3 days, such as Grade ≥ 3 ALT or AST (≥ 5 × ULN) with or without elevation of serum total bilirubin to > 2 × ULN, without initial findings of cholestasis (elevated serum alkaline phosphatase) or other apparent clinical causality.
 
	Temporarily interrupt treatment. Resume treatment (at the same dose) once severity resolves to Grade ≤ 1 or baseline. See Section 6.2.1 for dose delay allowances.	Temporarily interrupt RT during M3541 interruption. If interruption is longer than allowed in Section 6.2.1, RT without M3541 can be resumed at the discretion of the Investigator.		

CCI

	Dose Modific	ations
Toxicity	M3541ª	Radiotherapy b

 
Systemic Toxicities, Other
 
Nonhematologic Toxicities 
 
Any Grade ≥ 3 toxicity, excluding:
 
Diarrhea (≤ 3 days duration) following adequate and optimal therapy
 
Nausea and vomiting (≤ 3 days duration) with adequate and optimal therapy
 
Fatigue or headache (< 7 days duration) following initiation of adequate supportive care
 
Any other single laboratory values out of the normal range that have no clinical significance, and that resolve to Grade ≤ 2 with adequate measures within 7 days
 
 
 
	Temporarily interrupt treatment. Resume treatment (at the same dose) once severity resolves to Grade ≤ 1 or baseline. See Section 6.2.1 for dose delay allowances.	Temporarily interrupt RT during M3541 interruption. If interruption is longer than allowed in Section 6.2.1, RT without M3541 can be resumed at the discretion of the Investigator.

AE = adverse event; ALT = alanine aminotransferase; AST = aspartate aminotransferase; CTCAE V4.03 = Common Terminology Criteria for Adverse Events, Version 4.03; FD = fraction day; IMP = investigational medicinal product; RT = radiotherapy; ULN = upper limit of normal

Note: Severity of AEs will be graded using the CTCAE V4.03 toxicity grades.

- a As all treatments with M3541 will be given in combination with RT, an interruption in the administration of RT would lead to an interruption in treatment with M3541.
- b A maximum RT interruption of ≤ 3 FDs in total is allowed within the complete treatment period. If RT / M3541 treatment have been interrupted by more than > 3 radiotherapy days, the subject must be discontinued from M3541. All effort should be made to complete 10 FDs if possible.

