# 6.5.5 Management of Specific Adverse Events or Adverse Drug Reactions

No specific AEs or ADRs of particular concern have been identified. The Investigator should use clinical judgment and follow the guidelines in Table 7 the management of AEs / ADRs.

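### Table 7 holds M3541 and RT for isolated Grade 3 lymphocytopenia but not for isolated Grade 4

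*Protocol*

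**What the plan says.** The row at issue in Table 7 is headed "Systemic Toxicities Considered to be Unrelated to RT, Hematologic". Its trigger is any hematologic toxicity of Grade 3 or higher, less four exclusions:

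- "Neutropenia lasting for ≤ 5 days and not associated with fever"
- "Isolated Grade 4 lymphocytopenia without clinical correlate"
- thrombocytopenia of Grade 3 without bleeding
- anemia of any grade

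When the trigger is met, M3541 is interrupted and resumes at the same dose once the finding is back to Grade 1 or less, or to baseline. RT is interrupted for as long as M3541 is.

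The table is binding. Section 6.4.1 states: "The formal criteria for dose modification in the study are included in Table 7". Section 6.5.5 states: "The Investigator should use clinical judgment and follow the guidelines in Table 7".

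The length of a hold is limited. Footnote b of Table 7 reads "A maximum RT interruption of ≤ 3 FDs in total is allowed within the complete treatment period", and Section 6.2.1 says of the once per FD schedule: "If RT and M3541 treatment must be interrupted for ≥ 4 FDs, subjects must be discontinued from M3541".

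**The concern.** The exclusion names the more severe grade and leaves the milder one inside the trigger. A site following the table would delay palliative RT and M3541 for an isolated Grade 3 laboratory finding and treat straight through an isolated Grade 4. Neither document gives a reason for holding only the milder grade.

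The first thing at stake is treatment delivery, since the protocol asks for every effort to complete the 10 fractions. The second is the primary endpoint. A hold that reaches 4 FDs ends M3541 and, if the finding is related to study treatment, meets the interruption criterion for a DLT in Section 5.1.1. If it is not related, the subject may instead drop out of the DLT Analysis Set and be replaced.

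Section 6.5.4 names the lymphatic and hematopoietic systems among the main target organs of toxicity, so the line may well be used.

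**Working it through.** The plan states no figure on this point. The check is a literal reading of the rule, a search for text that overrides it, and a count of days.

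**1. The rule by grade** (isolated lymphocytopenia, no clinical correlate, judged unrelated to RT)

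| Grade at first detection | Grade ≥ 3? | Excluded? | Action |
|---|---|---|---|
| 1 or 2 | No | – | Continue |
| 3 | Yes | No | Hold M3541 and RT |
| 4 | Yes | Yes | Continue |

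The inversion concerns the grade at first detection. A subject already held at Grade 3 who worsens to Grade 4 has not met the resume condition and stays held. A subject first seen at Grade 4, not held, who improves to Grade 3 comes within the trigger on the literal text.

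**2. Text that might correct it**

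- The exemption beginning "Any other single laboratory values out of the normal range that have no clinical significance" is in the nonhematologic row, so it does not reach lymphocyte counts.
- Section 7.4.1.1 restricts which laboratory findings are reported as AEs. It does not separate Grade 3 from Grade 4. If it kept asymptomatic values out of Table 7 altogether, the Grade 4 exclusion would be unnecessary.
- Section 6.5.5 allows clinical judgment but still sends the Investigator to Table 7.
- The row is specific about grade elsewhere: Grade 3 only for thrombocytopenia, every grade for anemia. So naming Grade 4 cannot safely be read as including Grade 3.

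**3. Time to recover before M3541 is stopped**

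Inputs for the once per FD schedule: 3 missed FDs allowed in total (Table 7 footnote b), discontinuation at the fourth (Section 6.2.1), RT Monday to Friday. SAP Section 7 says the intermittent schedules were never explored. With no earlier interruption:

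| Hold starts | FDs missed | Latest resumption | Calendar days |
|---|---|---|---|
| Monday | Mon, Tue, Wed | Thursday | 3 |
| Tuesday | Tue, Wed, Thu | Friday | 3 |
| Wednesday | Wed, Thu, Fri | Monday | 5 |
| Thursday | Thu, Fri, Mon | Tuesday | 5 |
| Friday | Fri, Mon, Tue | Wednesday | 5 |

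An earlier interruption shortens these windows, because the 3-FD limit is cumulative. In the same row, neutropenia without fever is tolerated for up to 5 days with no hold; isolated Grade 3 lymphocytopenia is tolerated for 0 days.

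**4. What follows a hold of 4 FDs or more**

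- *M3541 and RT.* M3541 stops. RT alone may resume at the Investigator's discretion (Section 6.2.1, Table 7), so RT is delayed and not necessarily lost.
- *Related to study treatment.* The interruption criterion in Section 5.1.1 is met. The hematologic criterion there does not name lymphocytopenia at any grade, so an isolated Grade 4 that was not held becomes a DLT only if the SMC calls it one under the last criterion.
- *Not related.* With no earlier missed dose, a hold starting on FD *k* that ends M3541 leaves *k* − 1 doses given. Section 8.4 requires 8 of 10. Since *k* − 1 < 8 when *k* ≤ 8, a hold starting on any of FDs 1 to 8 takes the subject out of the DLT Analysis Set, and Section 5.5.2 requires replacement.

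**The case against.** The strongest reply accepts the literal reading and disputes its weight. Section 3.1.5 reports at most Grade 1 treatment-related toxicities so far. A hold of up to 3 FDs only lengthens the treatment period. The DLT route needs a finding that is Grade 3 at first detection, isolated, judged unrelated to RT, held for at least 4 FDs and related to study treatment. A sensible investigator who sees isolated Grade 4 exempted might treat Grade 3 the same way. All of this stands as a limit on size. It does not remove the contradiction, because it relies on sites departing from the table.

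The unrelated branch is also unusual: an event in this row that is not related to study treatment must be attributed to neither RT nor M3541 and still be handled as a toxicity. That stands too, and the consequence is conditional on it. The AE step has some circularity as well, since an asymptomatic value may become reportable only because the hold led to discontinuation.

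Finally, intent is not documented. Exempting Grade 3 only would also remove the inversion, would match the neighbouring thrombocytopenia line, and could be defended by the infection risk noted in Section 6.5.4. But it would create a Grade 4 hold that the sponsor has expressly waived. Exempting both grades keeps the tolerance already written and is the smaller change.

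**Conclusion.** The concern holds. As written, Table 7 holds M3541 and RT for a first-detected isolated Grade 3 lymphocytopenia and lets both continue for a first-detected isolated Grade 4. It should be corrected, because it is an operative hold rule that gives a perverse result when followed.

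The size is bounded only in part. The 3- or 5-day window assumes the once per FD schedule, Monday-to-Friday RT and no earlier interruption. It is not an estimate of how often M3541 would be stopped, because the documents give no lymphocyte recovery time. Frequency cannot be determined. No fixed effect on the MTD follows either, because the SMC decides how DLTs bear on the next dose. The inversion applies to the hold rule and not to every route to a DLT.

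**What to change.** Change the lymphocyte exclusion in the hematologic row of Table 7 to *Isolated Grade 3 or 4 lymphocytopenia without clinical correlate*. Neither grade would then trigger a hold on its own, and a Grade 4 improving to Grade 3 would not start one. A finding with a clinical correlate would still trigger a hold.

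The cost is a few words in one line, with no change to endpoint definitions, analysis sets or sample size. Because Table 7 holds the formal dose-modification criteria, the sponsor would need to decide under Section 10.5 whether the change is a substantive amendment requiring submission. If the sponsor did intend to hold at one grade and not the other, the protocol should say so and give the reason.
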